4.4. Eligibility Criteria for Randomization

Subjects must meet *all* of the following criteria to be eligible for randomization:

- 1) eGFR \geq 15 mL/min/1.73 m² at all central laboratory assessments during the Run-in period prior to Randomization (Visit 1)
- 2) At least 7 consecutive daily doses of SEL, without interruption, immediately prior to Visit C and prior to Randomization (Visit 1)
- 3) Subject did not permanently discontinue study drug during the Run-in period
- 4) Subject did not withdraw consent
- 5) Subject did not initiate, change dose, or discontinue SGLT-2 inhibitor during the Run-in period or is not anticipated to initiate, change dose or discontinue SGLT-2 inhibitor within 12 weeks after Randomization (Visit 1)
- 6) Negative urine pregnancy test for female subjects of childbearing potential
- 7) No ongoing clinically significant illness, medical condition, surgical history, physical finding, or laboratory abnormality that, in the investigator's opinion, could adversely affect the safety of the subject or impair the assessment of study results

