6.4.12. Estimated Glomerular Filtration Rate

- Screening: Subjects can have up to 3 eGFR collections during the Screening period. Any one of the eGFR values and any one of the UACR values collected during Screening may be used to satisfy the inclusion criteria. Subjects must have an eGFR value calculated by central laboratory utilizing samples collected during Screening and prior to Enrollment (Visit A) of ≥ 20 mL/min/1.73 m² to < 60 mL/min/1.73 m².
- Run-in period: Other than eGFR values < 15 mL/min/1.73 m², eGFR and serum creatinine results collected at Visit A, B, C, and Visit 1 will not be released to subjects, investigators or sponsor before study unblinding. Local labs assessing eGFR or creatinine should not be collected during the Run-in period or during the time after the Run-in period leading up to the Week 4 visit unless required for safety.
- Run-in prior to Week 4: If there is a $\geq 50\%$ decline in eGFR compared to Screening during the Run-in period prior to Week 4, a central laboratory flag will be issued to notify the site of this drop. Sites will be notified of the $\geq 50\%$ eGFR decline but will continue to be blinded to the eGFR values. Local labs assessing eGFR or creatinine should not be collected during the Run-in period or during the time after the Run-in period leading up to the Week 4 visit unless required for safety.

- Randomization: Subjects must have eGFR values of ≥ 15 mL/min/1.73 m² at all central laboratory assessments during the Run-in period to satisfy randomization eligibility.
- Stratification: eGFR will be the average of Enrollment (Visit A) and Visit B measurements. This value will be transferred directly from the central laboratory to the IWRS system for stratification.

A clinical endpoint event is a confirmed decrease in eGFR to < 15 mL/min/1.73 m² for subjects who remain asymptomatic without initiation of dialysis or kidney transplantation. The eGFR confirmatory measure will be collected at the next scheduled study visit but at least 4 weeks after the index measurement.

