8.5.2.2. Analysis of time from randomization to a Kidney Clinical Event

The $\geq 40\%$ decline in $eGFR_{cr}$ from baseline and sustained decrease in $eGFR_{cr}$ to < 15 mL/min/1.73 m² components need to be confirmed at the next scheduled visit but at least 4 weeks after the index measurement. Events of $eGFR_{cr} < 15$ mL/min/1.73 m² or $eGFR_{cr}$ decline $\geq 40\%$ from baseline without confirmation due to study discontinuation (e.g., death or lost to follow-up) will be included in the analysis. The date the first sample meets the threshold will be used as the date in the analysis.

If a subject has not experienced any Kidney Clinical Events at the time of global study end date/early discontinuation of the study, this subject will be censored at the time of the last assessment of kidney function.

The analysis of time from randomization to a Kidney Clinical Events will be conducted when all subjects in the ITT Analysis Set reach Week 48 or discontinue from the study. Baseline as well as all on- and off-treatment $eGFR_{cr}$ values collected after Visit 1 through the end of the study will be included in the evaluation of the endpoint. The comparison will be performed between the SEL and placebo arms using a stratified log-rank test, stratified by randomization stratification factors. Median survival times and 95% Confidence Intervals (CIs) for the SEL and placebo arms will be estimated using Kaplan-Meier method. Hazard ratio (HR) and 95% CI comparing the SEL and placebo arms will be estimated using a stratified Cox proportional hazard model, stratified by randomization stratification factors.

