- i. eGFR value to be calculated by the Chronic Kidney Disease Epidemiology Creatinine Equation (2009); if eGFR value at Screening does not meet inclusion criteria, subject may repeat 2 additional times during Screening and prior to Enrollment (Visit A). Subject must have eGFR ≥ 15 mL/min/1.73 m² at all central laboratory assessments during the Run-in period prior to Randomization (Visit 1)
- j. First morning void collection is preferred when possible, but early morning void is accepted. Bring sample to clinic within 1 hour, if not possible, refrigerate and bring to clinic within 12 hours. If UACR value at Screening does not meet inclusion criteria, subject may repeat 2 additional times during Screening and prior to Enrollment (Visit A)
- k. [REDACTED]
- l. For subjects taking digoxin only, digoxin level should be measured at Visit C and Week 4. PI may continue checking after Week 4 as part of digoxin management as needed. Monitor and adjust digoxin dose as necessary based on prescribing information.
- m. Females of childbearing potential as defined by protocol only (refer to [Appendix 6](#)): Serum pregnancy test at Screening and urine pregnancy test at Visit B, Randomization and every 4 weeks through the 30 Day EOT Follow-up visit.
- n. FSH testing to determine female subject's postmenopausal state as described in [Appendix 6](#).

Study Procedures Table – Week 4 to Week 48+

	Period	On Treatment						
	Visit	2	3	4	5	6	7	q12 weeks ¹
	Week	4	8	12	24	36	48	
	Visit Window (days)	±5	±5	±5	±5	±5	±5	
Complete Physical Examination ^a								
Vital Signs including Weight ^b	X	X	X	X	X	X	X	X
Waist Circumference							X	
12 Lead ECG							X	
Clinical Assessments	CCI							
	CCI							
	CCI							
	Adverse Events	X	X	X	X	X	X	X
	Concomitant Medications	X	X	X	X	X	X	X
	Study Drug Dispensing	X	X	X	X	X	X	X
	Study Drug Dosing	X	X	X	X	X	X	X
	Study Drug Bottle Return	X	X	X	X	X	X	X

	Period	On Treatment						
	Visit	2	3	4	5	6	7	q12 weeks ¹
	Week	4	8	12	24	36	48	
	Visit Window (days)	±5	±5	±5	±5	±5	±5	±5
Laboratory Assessments	Subject Fasting ^e						X	
	eGFR ^f	X	X	X	X	X	X	X
	Early Morning Void Urine ACR & Urinalysis ^g	X	X	X	X	X	X	X
	Chemistry & Hematology	X	X	X	X	X	X	X
	HbA1c				X		X	X
	Blood Biomarkers	X			X		X	
	Insulin, Lipid, c-peptide						X	
	Nt-proBNP						X	
	cTnI						X	
	Digoxin ^h	X						
	CRP						X	
	Sparse PK ⁱ	X		X	X		X	
	CCI							
Pregnancy Testing ^k	X	X	X	X	X	X	X	
Urine Biomarkers	X			X		X		

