6.2. Secondary Endpoints

6.2.1. Definition of Secondary Endpoints

Secondary endpoints for this study are:

- Proportion of Kidney Clinical Events defined as any of the following events:
 - Confirmed $\geq 40\%$ decline in eGFR_{cr} from pre-run-in Baseline, or
 - Kidney failure (dialysis performed for at least 4 weeks, kidney transplantation, or confirmed decrease in eGFR_{cr} to < 15 mL/min/1.73 m² for subjects without dialysis or kidney transplantation), or
 - Death due to kidney disease

The $\geq 40\%$ decline in $eGFR_{cr}$ from Baseline and sustained decrease in $eGFR_{cr}$ to <15 mL/min/1.73 m² components need to be confirmed at the next scheduled visit but at least 4 weeks after the index measurement (i.e., the first measurement of $\geq 40\%$ decline in $eGFR_{cr}$ from Baseline or $eGFR_{cr} < 15$ mL/min/1.73 m²). Events of $eGFR_{cr}$ decline $\geq 40\%$ from Baseline or $eGFR_{cr} < 15$ mL/min/1.73 m² without confirmation due to study discontinuation (e.g., death or lost to follow-up) will be included in the analysis and counted as events. Date of the index measurement will be used as the date of event in the analysis.

- Time from randomization to first occurrence of a Kidney Clinical Event

If a subject has not experienced any Kidney Clinical Events at the time of global study end date/early discontinuation of the study, this subject will be censored at the time of the last assessment of kidney function.

- $eGFR_{cys}$ slope from pre-run-in Baseline through Week 84

The values for $eGFR_{cys}$ will be calculated using the CKD-EPI Cystatin C Equation (2012):

$$eGFR = 133 \times \min\left(\frac{S_{cys}}{0.8}, 1\right)^{-0.499} \times \max\left(\frac{S_{cys}}{0.8}, 1\right)^{-1.328} \times 0.996^{Age} \times 0.932[if\ female]$$

S_{cys} = standardized serum cystatin C (mg/L)

min indicates the minimum of $S_{cys}/0.8$ or 1

max indicates the maximum of $S_{cys}/0.8$ or 1

age in years

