6.2.2.2. Analysis of time from randomization to a Kidney Clinical Event

A stratified log-rank test stratified by randomization stratification factors will be used to evaluate SEL treatment effect on time from randomization to a Kidney Clinical Event. Hazard ratio (HR) and 95% CI comparing the SEL and placebo arms will be estimated using a stratified Cox proportional hazard model, stratified by randomization stratification factors. Number and percent of subjects with event per treatment group, event rate, HR, 95% CI and p-value will be presented for analysis of time to the first Kidney Clinical Event, and time to each component of the Kidney Clinical Event endpoint. HR and 95% CI will only be reported for outcomes with more than 10 events, and have at least 1 event in each treatment arm. Event rate will be calculated as the number of subjects with the event, divided by the total duration of follow-up across all subjects in a given treatment group. Follow-up time for each subject will be calculated as time from Randomization to the earliest of study completion, premature study discontinuation, death and event of interest for a given outcome.

Sensitivity analyses will be performed based on different definition of events or population.

The same approaches as described in Sections 6.2.2.1 and 6.2.2.2 will be used for hypothesis testing for Kidney Clinical Events for the following:

- Sensitivity analysis where in the SEL group, a 40% reduction in $eGFR_{cr}$ will be calculated from the pre-run-in Baseline $eGFR_{cr}$ for off-treatment $eGFR_{cr}$ values and the post-run-in Baseline $eGFR_{cr}$ for on-treatment $eGFR_{cr}$ values.
- Sensitivity analysis to use treatment-specific Baselines to calculate $eGFR_{cr}$ percent decline. For all $eGFR_{cr}$ values in the SEL group, a 40% reduction in $eGFR_{cr}$ will be calculated using the post-run-in Baseline $eGFR_{cr}$.

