- Sensitivity analysis to evaluate the impact of attenuation of the acute effect. For subjects in the SEL group, the on-treatment $eGFR_{cr}$ values will be adjusted using a regression model as described in [Appendix 2](#), which takes into account attenuation of the acute treatment effect that may be due to the theoretical concern for loss of kidney function over time. This adjusted on-treatment $eGFR_{cr}$ value will be compared with the pre-run-in Baseline $eGFR_{cr}$ to calculate an adjusted percent $eGFR_{cr}$ reduction. For subjects in the placebo group, percent $eGFR_{cr}$ reduction will be calculated by comparing observed $eGFR_{cr}$ values with the pre-run-in Baseline $eGFR_{cr}$.
- Sensitivity analysis in subjects who completed study treatment.
- Sensitivity analysis excluding subjects with randomization stratification mismatch between IXRS and Clinical Database.
- Sensitivity analysis excluding subjects who took prohibited medications that may affect SEL efficacy or decrease SEL drug level in the prohibited period as detailed in [Appendix 3](#).

- Sensitivity analysis where a 57% reduction in $eGFR_{cr}$ from pre-run-in Baseline will be used for the $eGFR_{cr}$ reduction component of the Kidney Clinical Events instead of 40% reduction.
- Sensitivity analysis for the Kidney Clinical Events based on $eGFR_{cys}$. The Kidney Clinical Events endpoint will have the same definition as in Section 6.2.1, except that the $eGFR$ reduction and $eGFR < 15$ components will be based on $eGFR_{cys}$ instead of $eGFR_{cr}$.

The same approaches as described in Sections 6.2.2.1 only will be used for hypothesis testing for Kidney Clinical Events for the following:

- The proportion of Kidney Clinical Events by Week 48 will be compared between SEL and placebo treatment arms. Subjects who do not have sufficient measurements to determine whether or not they had a Kidney Clinical Event by Week 48 will be considered not having a Kidney Clinical Event by Week 48.

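### The eGFRcys sensitivity analysis of the Kidney Clinical Event has no baseline condition on its below-15 component, so a subject already below 15 by cystatin C could be counted as a new kidney failure at Week 4

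*SAP*

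**What the plan says.** **Entry.** Inclusion criterion 3 (Protocol 4.2) requires a screening eGFR of 20 to below 60, calculated with the CKD-EPI creatinine equation. Protocol 4.4 requires eGFR of at least 15 "at all central laboratory assessments during the Run-in period prior to Randomization (Visit 1"). Protocol 6.4.12.1 computes unqualified eGFR from serum creatinine. The Appendix 2 footnote that repeats the at-least-15 rule opens with "eGFR value to be calculated by the Chronic Kidney Disease Epidemiology Creatinine Equation (2009"). No visible criterion uses cystatin C.

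**Main event definition (SAP 6.2.1).** Kidney failure includes a confirmed decrease in eGFRcr to below 15. The eGFR components "need to be confirmed at the next scheduled visit but at least 4 weeks after the index measurement", and the index is described as the first measurement at or past the threshold. "Date of the index measurement will be used as the date of event in the analysis". A qualifying value left unconfirmed because the subject leaves the study still counts.

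**Cystatin C version (SAP 6.2.2.2).** "The Kidney Clinical Events endpoint will have the same definition as in Section 6.2.1", except that eGFRcys replaces eGFRcr in both eGFR components. It is in the list introduced by "The same approaches as described in Sections 6.2.2.1 and 6.2.2.2 will be used for hypothesis testing for Kidney Clinical Events for the following", so it gets the CMH and Fisher tests, the stratified log-rank test and the Cox model. No baseline condition is added.

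**The concern.** For the creatinine endpoint, the run-in rule does work that the event definition leaves unstated. Every randomized subject should have had eGFRcr of at least 15 at each run-in assessment, so a later confirmed value below 15 is a change. When the same definition is moved to cystatin C, that protection is lost. A subject can satisfy every creatinine criterion and still have eGFRcys below 15 at Visits A and B.

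If such a subject is counted, the event says nothing about treatment. It enters both arms at the same expected rate and draws the treatment contrast towards no effect. The kidney-failure component is most exposed, because its counts are likely to be small and SAP 6.2.2.2 reports a hazard ratio only for outcomes with more than 10 events and at least one in each arm. A few prevalent cases could carry that component over the reporting threshold.

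**Working it through.** **The plan's own figures.** The documents give no event rate, no baseline eGFRcys distribution and no power for this analysis. The only sizing figure is for the primary slope (difference 3.7, SD 10, one-sided 0.15). It reproduces: 98.5% at 150 per arm and 97.2% at 127 per arm, against the stated 99% and 97%. Nothing below touches it.

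**Step 1: timeline for a subject below 15 by cystatin C throughout.**

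- Protocol 8.5.2.2 states, for eGFRcr, that "values collected after Visit 1 through the end of the study will be included in the evaluation of the endpoint". With post-randomization visits at Weeks 4, 8, 12, 24 and on, the first scheduled candidate is Week 4, which becomes the index.
- The next scheduled visit is Week 8. If it falls at least 4 weeks after the index, the event is confirmed.
- The event is dated at the index, Week 4. The path is the same in both arms.

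**Step 2: can eGFRcr be 20 while eGFRcys is below 15?** Using the protocol's equations for a non-Black man of 65:

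- eGFRcr = 141 × 0.993^65 × (Scr/0.9)^−1.209, and 141 × 0.993^65 = 89.3. So eGFRcr 20 is Scr = 0.9 × (89.3/20)^(1/1.209) = 3.10 mg/dL.
- eGFRcys = 133 × 0.996^65 × (Scys/0.8)^−1.328, and 133 × 0.996^65 = 102.5. So eGFRcys 20 is Scys 2.74 mg/L and eGFRcys 15 is Scys 3.40 mg/L.

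At eGFRcr 20, eGFRcys is below 15 when it is less than 0.75 times eGFRcr.

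**Step 3: how many? (assumptions, not document figures)** Let ln(eGFRcys/eGFRcr) be normal with mean m and SD s. Then P(eGFRcys < 15 | eGFRcr = g) = Φ((ln(15/g) − m)/s). For m from 0 to −0.10 and s from 0.15 to 0.25 this is 2.8% to 22.6% at g = 20, 0.03% to 5.0% at g = 25, and at most 0.9% at g = 30. The exposure lies mainly in the lowest eGFR stratum.

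Averaging over eGFRcr ~ N(35, 10), truncated:

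| m | s | truncated to 20–60: share (of 300) | truncated to 15–60: share (of 300) |
|---|---|---|---|
| 0 | 0.15 | 0.06% (0.2) | 0.77% (2.3) |
| 0 | 0.25 | 0.70% (2.1) | 1.83% (5.5) |
| −0.10 | 0.15 | 0.28% (0.8) | 1.79% (5.4) |
| −0.10 | 0.25 | 1.57% (4.7) | 3.28% (9.8) |

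The right-hand column is included because the lowest randomization stratum runs from 15 and uses the Visit A and B average, so eGFRcr may have fallen below the screening limit of 20.

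**Step 4: dilution (risks assumed).** Let a share q start below 15, all be counted, and otherwise carry average risk. Each arm's observed risk is q + (1 − q)p, so the risk difference is multiplied by (1 − q). With true risks of 15% (placebo) and 10% (SEL):

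| q | observed risks | difference (points) | risk ratio | prevalent share of events | power, one-sided 0.15, 150 per arm |
|---|---|---|---|---|---|
| 0 | 15.0% / 10.0% | 5.00 | 0.667 | 0% | 61% |
| 1.6% | 16.4% / 11.4% | 4.92 | 0.699 | 11.5% | 58% |
| 3.3% | 17.8% / 13.0% | 4.84 | 0.728 | 21.4% | 55% |

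This somewhat overstates the dilution. Subjects below 15 by cystatin C are likely to be among those nearest to kidney failure, and some would have had an event anyway.

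**The case against.** **The wording may already exclude these subjects.** The component is a decrease to below 15; Protocol 6.4.12 likewise says "A clinical endpoint event is a confirmed decrease in eGFR to" below 15. A subject who was never above 15 has not decreased to it. This is a fair reading, and it means the documents do not establish that such subjects will be counted. But SAP 6.2.1 describes the index simply as the first measurement below 15 and writes no baseline condition, so the other coding is equally defensible. The ambiguity stands. Nor is the event automatic: confirmation, or leaving the study before it, is required, and a subject whose eGFRcys rises to 15 or more at the confirming visit would not count.

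**The numbers are small and assumed.** This stands. A reader might infer a larger problem by setting every simulated eGFRcr below 20 to exactly 20. That gives 0.24% to 2.95% (1 to 9 subjects) under the same inputs, but it places 6.7% of the trial at the value where eGFRcys below 15 is most likely. Truncation is the faithful form of a 20-to-60 limit.

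**The stakes are low.** This also stands. It is one of eight sensitivity analyses of secondary endpoints that share both event methods, and no decision rule is attached to it. A reader might regard it as the only event analysis that deals with the acute creatinine effect. It is not: the two baseline-switching analyses and the Appendix 2 adjustment also address that effect, though they still use creatinine.

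**The remedy departs from keeping the definition identical.** True, for a few subjects and one component.

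**Conclusion.** The gap is real and minor. SAP 6.2.2.2 carries the below-15 component over to eGFRcys without the baseline protection that creatinine-based entry gave the main endpoint. A subject persistently below 15 by cystatin C could be counted as a kidney failure dated Week 4.

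The likely number is 0 to 5 of 300 (0.05% to 1.6%), or 2 to 10 (0.8% to 3.3%) if eGFRcr may be as low as 15 before randomization. Both ranges rest on an assumed eGFRcr distribution and an assumed cystatin-to-creatinine ratio. Under the illustrative risks, the risk difference moves by less than 0.2 points. The kidney-failure component would feel it most.

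A reader might infer that the defect favours one arm, inflates type I error or weakens the main results. The documents do not support that. The cases are balanced by randomization on average, so they dilute rather than bias the test towards a false positive. The main Kidney Clinical Event uses eGFRcr, for which the run-in rule applies. The primary endpoint and the stated power are untouched.

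**What to change.** Add to the eGFRcys bullet in SAP 6.2.2.2: *the eGFRcys < 15 component applies only to subjects with pre-run-in Baseline eGFRcys ≥ 15; subjects below 15 at Baseline can qualify through a ≥ 40% decline in eGFRcys, dialysis, transplantation or death due to kidney disease.* Report by arm how many subjects start below 15, so that readers can judge the effect whichever way it is coded.

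No new data are needed: cystatin C is in the chemistry panel, and SAP 3.8.3 already provides for a pre-run-in Baseline for eGFRcys. The cost is one sentence and one table row. The small downside is that these few subjects have one component fewer than the rest. Because the condition uses the Visit A and B average, a subject averaging just above 15 but below it at a single run-in visit could still be counted.

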6.2.2.3. Analysis of $eGFR_{cys}$ slope from pre-run-in Baseline

A random slope model will be used to evaluate SEL treatment effect on $eGFR_{cys}$ slope from pre-run-in Baseline through Week 84. The random slope model will have change in $eGFR_{cys}$ values from pre-run-in Baseline at Weeks 4, 8, 12, 24, 36, 48, 60, 72, and 84 as outcome, and will include terms for pre-run-in Baseline $eGFR_{cys}$ as a continuous variable, pre-run-in Baseline UACR category (< 1500 mg/g vs. ≥ 1500 mg/g), concomitant use of SGLT-2 inhibitors at Randomization, treatment group, week, and treatment-by-week interaction. Within-subject variance covariance will be modeled as unstructured. If model convergence problems arise, other variance-covariance structures, such as Heterogeneous Toeplitz, will be considered and documented.

Sensitivity analyses of the $eGFR_{cys}$ slope endpoint will include the following:

- Sensitivity analysis of $eGFR_{cys}$ slope excluding $eGFR_{cys}$ values collected after the initiation of dialysis or kidney transplantation.
- Sensitivity analysis of $eGFR_{cys}$ slope in subjects who completed study treatment.
- Sensitivity analysis of $eGFR_{cys}$ slope excluding subjects with randomization stratification mismatch between IXRS and Clinical Database.
- Sensitivity analysis of $eGFR_{cys}$ slope excluding subjects who took prohibited medications that may affect SEL efficacy or decrease SEL drug level in the prohibited period as detailed in [Appendix 3](#).
- Sensitivity analysis of $eGFR_{cys}$ slope from pre-run-in Baseline through Week 48.
- Sensitivity analysis of $eGFR_{cys}$ slope from pre-run-in Baseline through Week 60.
- Sensitivity analysis of $eGFR_{cys}$ slope from pre-run-in Baseline through Week 72.
- Sensitivity analysis of $eGFR_{cys}$ slope from pre-run-in Baseline through Week 96.

CCI

[REDACTED]

[REDACTED]

[REDACTED]

[REDACTED]

[REDACTED]

[REDACTED]

[REDACTED]

[REDACTED]

[REDACTED]

[REDACTED]

[REDACTED]

CCI [Redacted]

[Redacted]

[Redacted]

[Redacted]

[Redacted]

[Redacted]

[Redacted]

[Redacted]

CCI
[Redacted]

[Redacted]

[Redacted]

[Redacted]

[Redacted]

[Redacted]

[Redacted]

CCI
[Redacted]

[Redacted]

[Redacted]

[Redacted]

[Redacted]

[Redacted]

[Redacted]

[Redacted]

[Redacted]

CCI
[Redacted text block]

